Study Protocol and Statistical Analysis Plan

Unique Protocol ID: EA200329

Brief Title: Enhancing Mother-Child Ties and Psychosocial Wellness Through Arts Among Children With Intellectual Disability and Their Mothers

Official Title: Enhancing Mother-Child Ties and Psychosocial Wellness Through Arts: A Mixed Methods Study on Dyadic Expressive Arts-based Intervention for Children With Intellectual Disability and Their Mothers

Document Creation Date: April 25, 2024

Document version: 5

Enhancing Mother-Child Ties and Psychosocial Wellness through Arts: A Mixed Methods Study on Dyadic Expressive arts-based Intervention Group for Children with Intellectual Disability and their Mothers

Background: Caregiving mothers of children with intellectual disability (ID) are vulnerable to caregiver stress and burnout. Children with ID may have difficulty in expressing emotions, thus imposes additional challenges for the parents to understand and interact with them. Existing intervention programs for families having children with ID focus on problem- and emotion-focused measures, while strategies focusing on improving parent-child relationships, mother-child communication and wellness of the dyads are limited. Expressive arts-based intervention (EXAT) can bypass verbal expression and cognition during interaction, and is also an engaging, enjoyable, and safe process of empowerment. Although evidence has supported the use of arts-based interventions for children with disabilities and for parents alone, there is a lack of evidence on multimodal dyadic EXAT on the mother-child interaction, their relationship and wellness.

Objectives: The present study aims to investigate the effectiveness of the dyadic EXAT group on psychosocial outcomes of children with ID and their caregiving mother. Primary outcomes include parent-child relationship, parenting stress, and caregiver burnout; secondary outcomes include mother's affect and quality of life; child's mood, emotional expression, behavioral and emotional problems.

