Research ethics: Ethical approval will be obtained from the Institutional Review Board and Human Research Ethics Committee prior to data collection, and consent will be obtained from all recruited participants (the mothers, and children with ID) prior to assessment. The study will be registered in the ClinicalTrials.gov under the National Institutes of Health, and the HKU Clinical Trials Registry.

Measurements

Mother's psychosocial outcomes and perceived parent-child relationship

- 1. *Parenting stress*. The 36-item Parenting Stress Index (4th Ed, Short-form) (PSI/SF) [41] will be used to assess parenting stress of the mothers on 3 domains: (i) parental distress, (ii) parent-child dysfunctional interaction, and (iii) difficult child. The index reported an internal consistency of .92, and has been adopted in local studies of mothers with children having special education needs [42]. Higher scores indicate higher parenting stress.
- 2. Caregiver burnout. The 6-item client burnout subscale of the Copenhagen Burnout Inventory [43] will be used to measure the mothers' caregiving burnout. This scale has a central focus on fatigue and exhaustion which matches the definition of burnout; and this scale has been validated with good reliability in local context and has been used in a study on Chinese caregivers of individuals with ID [44]. The subscale used is rated on a 5-point Likert format ranging from 0 ("never/ to a very low degree") to 100 ("always/ to a very high degree"), with higher scores indicating higher levels of burnout.
- 3. Parent-child relationship. The subscales of parent-child communication (9 items) and satisfaction with parenting (10 items) from the Parent-Child Relationship Inventory (PCRI) will be used to measure the mother's perceived attitude towards parent-child relationship [45]. The items are rated on a 4-point Likert Scale from (1) strongly agree to (4) strongly disagree; and negative items are reversed coded. Higher scores indicate positive perception of the specific dimensions of parenting perceived by the caregiving mother. The research

- team will undertake the authorized translation of the subscales.

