- 4. *Positive and negative affect*. The 10-item International Positive and Negative Affectivity Schedule Short Form [46] measures positive and negative affectivity of the mothers on a 5-point Likert format, ranging from 1 ("Never") to 5 ("Always"). The scale yields positive affect and negative affect subscales. Higher scores in each subscale indicate more of that affective state for the respondent.
- 5. *Quality of life*. The 28-item WHO Quality of Life Scale, Brief version (WHOQOL-BREF) [47] addresses physical, psychological, social, and environmental quality of life. The Chinese version has been adopted in a study of caregiver burden of parents with children having ID scores denoting better quality of life in a specific domain.
- 6. *Psychological well-being*. The 5-item World Health Organization Five Well-Being Index (WHO-5) [48] measures the subjective psychological well-being on a Likert scale, ranging from 5 ("All of the time") to 0 ("At no time") in the past 2 weeks. Raw score is converted to a percentage scale to provide a score of 0 to 100. Higher scores reflect higher subjective well-being.

Children's psychosocial outcomes

- 7. *Mood states*. The Ottawa Mood Scales are a series of Likert scales desinged to help children express how they feel [49]. The scale is composed of 5 items which assess mood, anger, worry, stress and self-regulation. For self-regulation, there are faces depicting the corresponding emotional states and a thermometer icon represent the arousal state at the bottom. For mood, anger, worry and stress, there is a numerical scale with schematic faces showing the corresponding emotions. The tool has been valdiated to use in a Malaysian young adult sample [50]. The research team will undertake the translation of this scale.

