- 8. *Emotional expression*. The Face Stimulus Assessment [51] is an arts-based projective assessment which is a viable means of extracting psychological information including emotional expressions for individuals with communication difficulties, including ID [52]. The assessment contains a series of three A4-size stimulus drawing templates: the first is a pre-drawn face, the second is a face outline, and the third is a blank sheet of paper. Participants will be asked to use the markers provided on the templates individually. The FSA will be administered in small groups and assessed through a quantitative and qualitative approach following guidelines from the FSA E-Packet and Rating Manual (2nd ed.) [51, 53]. The artworks will also be digitally scanned to analyze the pattern of color usage [1]. This assessment will be conducted by a trained Expressive Arts Therapist, a EXAT Trainee under supervision, or a trained research staff.
- 9. Behavioral and emotional problems. The 113-item Child Behavior Checklist (Teachers' Report Form) measures behavioral and emotional behaviors related to child functioning and problem behaviors observed by the teachers/professionals [54]. The Chinese version is widely adopted in Hong Kong with established local norms [55]. School teachers or social workers of the participating children will be invited to fill in the checklist and indicate the degree or frequency of the behaviors described in the checklist on a scale of 0 (not true), 1 (somewhat or sometimes true), or 2 (very true or often true). The checklist yields three composite scores on externalizing, internalizing, and total behavioral problems, and eight syndromes of withdrawn, somatic complaints, anxious/depressed, thought problems, social problems, attention problems, deliquent behaviors, and aggressive beahvior with higher scores indicating greater manifestations of the described behavior problems in the area [56].

Other variables

10. *Demographics*: Participant profile including age, gender, education level, income, employment status, religiosity, marital status, and family composition will be recorded. Clinical information (time since onset/ diagnosis, medical treatment record, psychiatric

history, comorbidity (physical disabilities, hypertension, diabetes mellitus, or other cognitive disturbance) and history of rehabilitation service utilization of the parents and children will be documented.

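### As printed, the scoring rule for the parent-child relationship inventory makes low scores favourable, while the next sentence says higher is better

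*Combined protocol and SAP*

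**What the plan says.** The Objectives name the outcome as primary: "Primary outcomes include parent-child relationship, parenting stress, and caregiver burnout". It is measured with two PCRI subscales, parent-child communication (9 items) and satisfaction with parenting (10 items).

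Measurements, item 3 makes three statements about them:

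- Anchors and recoding: "The items are rated on a 4-point Likert Scale from (1) strongly agree to (4) strongly disagree; and negative items are reversed coded".
- Direction: "Higher scores indicate positive perception of the specific dimensions of parenting perceived by the caregiving mother".
- Language version: the research "team will undertake the authorized translation of the subscales".

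The document contains no list of negative items, no scoring key and no final reversal of the total. It does not say whether items are summed or averaged. PCRI scoring is not restated anywhere else.

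**The concern.** Reverse coding is meant to make every item point the same way, and here it does. With agreement coded low and only the negatively worded items reversed, however, that way is low = favourable, the opposite of the stated direction.

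An analyst who codes the rule as printed and interprets the group-by-time estimate as the next sentence directs would report benefit as harm, or harm as benefit, on a primary outcome. The tests are two-tailed (Data Analysis, item 1), so neither the p-value nor the absolute effect size would give any warning. Because the team is producing the translation itself, the anchors on the form the mothers actually complete also need confirming.

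**Working it through.** **Inputs (Measurements, item 3).** Strongly agree = 1, strongly disagree = 4; 9 and 10 items; negative items reversed. On a 1–4 scale, reversal is 5 − response. Summing is my assumption; with averaging, the direction is the same. The plan states no PCRI score to reproduce, so the check applies its rule to the two extreme respondents.

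**Rule as printed, *negative* taken as negatively worded.** Let a subscale have *n* items, *p* of them positively worded.

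- Most favourable mother (agrees strongly with every positive item, disagrees strongly with every negative one): *p* × 1 + (*n* − *p*) × (5 − 4) = *n*.
- Least favourable mother: *p* × 4 + (*n* − *p*) × (5 − 1) = 4*n*.

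Neither result depends on *p*, so both hold for all 10 + 11 = 21 possible mixes (0–9 positive items of 9; 0–10 of 10). No knowledge of the item wording is needed.

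| Coding | Communication, most / least favourable | Satisfaction, most / least favourable | Higher = better? |
|---|---|---|---|
| As printed: 1 = agree, reverse negatively worded items | 9 / 36 | 10 / 40 | No |
| 1 = agree, reverse positively worded items | 36 / 9 | 40 / 10 | Yes |
| 1 = disagree, reverse negatively worded items | 36 / 9 | 40 / 10 | Yes |

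**Effect on the estimate.** Each literally coded item equals 5 minus its direction-consistent value. The literal sum is therefore 5*n* minus the consistent sum: 45 − *x* for communication and 50 − *x* for satisfaction. Subtracting from a constant leaves the SD unchanged and reverses the difference in means. Cohen's *d* becomes −*d*, and |*t*| and the two-sided p-value stay the same. At the effect of 0.5 used under Sample Size, +0.5 would be reported as −0.5, a gap of 0.5 − (−0.5) = 1.0 SD.

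**Path analysis (Data Analysis, item 2).** Where parent-child relationship is the mediator, the path into it and the path out of it both change sign. Since (−a)(−b) = ab, the indirect effect is unchanged, although each path would be misread.

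**Other instruments in the section.** Four others print both anchors and a direction, and in all four the two agree:

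- Burnout subscale: 0 = never to 100 = always, "with higher scores indicating higher levels of burnout".
- Affect schedule: 1 = never to 5 = always. "Higher scores in each subscale indicate more of that affective state for the respondent".
- WHO-5: 5 = all of the time to 0 = at no time. "Higher scores reflect higher subjective well-being".
- Teachers' Report Form: "on a scale of 0 (not true), 1 (somewhat or sometimes true), or 2 (very true or often true"), with higher scores meaning more problems.

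The PCRI is the one exception among five.

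**The case against.** The strongest defence is that *negative items* may mean items keyed against the stated direction. With agreement coded 1, those are the positively worded ones; reversing them gives 36 and 40 for the most favourable mother, and the conflict disappears. Item 3 is also a short description of a published instrument rather than a programming specification, and a team working from an authorized translation would probably score from the instrument's own key. On this view the point is a matter of wording. The documents cannot exclude that reading, but they do not state it, and a rule that works only if *negative* means positively worded should be rewritten in either case.

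Several narrower objections stand:

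- A wrong sign in the report needs two things: literal coding, and an interpretation in the stated direction that nobody questions. The documents show neither.
- The 0.5 is a general planning value for the primary outcomes, not an estimate for the PCRI, so the 1.0 SD gap is only illustrative.
- The other four instruments use frequency, degree or true/not-true anchors, and no reverse-coded items are mentioned for them. The comparison shows that the section does not habitually print anchors against direction, and no more. The contradiction rests on item 3 alone.

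There is also a partial safeguard. The interviews ask about change in the relationship (Appendix D, question 2), and their themes are compared with the quantitative results. But the interviews cover only 30 mothers, all from the intervention arm (Study Design), and the comparison is not a scoring check.

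**Conclusion.** The concern holds. On the ordinary meaning of its words, the printed rule produces a score on which low is favourable, for every possible mix of items, and the next sentence says the reverse. The intended direction (higher = better) is clear from item 3; the coding printed there does not deliver it.

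The consequence is conditional: a reversed sign on a primary outcome if the rule is followed literally and read as directed, with the p-value, absolute effect size and indirect effect unchanged. It is recoverable from the raw answers, and nothing shows that it has happened. The finding rests on reading *negative* as negatively worded. The documents do not show whether the anchors or the reversal rule is the misprint. It should be fixed because the outcome is primary and the correction costs almost nothing.

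**What to change.** Before any between-group analysis, check the response coding on the translated form as administered and the instrument's scoring key, then correct Measurements, item 3 to match:

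- If the form runs from 1 = strongly agree, state that positively worded items are reversed (5 minus response) and negatively worded items are left as answered.
- If the form runs from 1 = strongly disagree, correct the printed anchors and keep the reversal of negatively worded items.

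In either case, list the reversed items by number for each subscale and state whether items are summed or averaged. The form and the key decide. A blinded, pooled baseline correlation with the parent-child dysfunctional interaction domain of the Parenting Stress Index, expected to be negative, could serve as an optional backstop.

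The cost is a look-up, one or two corrected sentences and an item list, with no new data and no change to the design or sample size. Making the correction before results are seen also avoids changing the direction of a primary outcome after the fact.

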Method: The present study adopts a mixed-methods design with quantitative, qualitative, and arts-based assessment methods. 154 Chinese parent-child dyads (77 dyads in each arm), composing of a child (6-12 years) with mild to moderate ID, and the caregiving mother, will be randomized into (i) a dyadic EXAT group or (ii) treatment-as-usual, waitlist control group. The dyads will be assessed on a questionnaire packet at baseline (T_0), post-intervention (T_1), 3-month post-intervention (T_2), and 6-month post-intervention (T_3). A random subsample of mothers (N=30) will be invited to attend in-depth two in-depth interviews at T_1 and T_3 for understanding the experiences, perceived changes, and factors that are attributable to how the intervention achieves its intended goals. Data collected will be triangulated to provide an integrative evaluation to the effectiveness of the intervention.

Significance: This is a pioneer study exploring the benefits of dyadic EXAT on mother-child relationship of children with ID, and their psychosocial wellness. This rigorous scientific inquiry on the effectiveness of dyadic EXAT in this population can provide empirical support to EXAT as an evidence-based, relationship-focused intervention to help these families cope. Results of the study could establish EXAT as an evidence-based practice for these families and the potential to apply to other populations with children having developmental disorders, disabilities, or special education needs.

Keywords: Mother-child relationship, Psychosocial Well-being, Expressive Arts Therapy, Intellectual disability, Randomized controlled trial

Project Objectives (max. 800 words)

Project Objectives

The **primary objective** of the present study is to investigate the effectiveness of a dyadic Expressive arts-based intervention with reference to a waitlist control group on the caregiving mother on the following domains:

- (i) Parenting stress;
- (ii) Caregiver burnout, and;
- (iii) Parent-child relationship;

The **secondary objective** of the proposed study also aims to investigate the effectiveness of the dyadic Expressive arts-based intervention on other psychosocial wellness of the caregiving mothers and children:

- (iv) Mother's positive and negative affect
- (v) Children's mood (as indicated by a visual analogue);
- (vi) Emotional expressions (as indicated by arts-based assessment);
- (vii) Behavioral and emotional problems (as perceived by the teachers or social workers);

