Participants. Participants are mother-child dyads composing of a mother caregiver and a child who is aged 6-12 years (primary school student) and fulfils the diagnostic criteria for *mild* grade to moderate grade ID (based on the age-relevant IQ test assessments administered by a qualified professional). In the judgment of health/school professional staff, the child is capable of responding to assessments and participating in group activities. The dyads are able and willing to give consent for participation in the study (guardian's assent consent will be arranged for the participating children, while written consent will obtained from the adult mothers). Dyads are excluded if: (i) the dyad is currently participating in any other behavioral or pharmacological trial, and/or (ii) either member of the dyads have other contraindications or severe comorbidities that may impair their full participation (e.g. severe physical disabilities).

Recruitment. The recruitment will be facilitated by our collaborative partners in the community (including SEN schools, and community-based units that serve families of children with ID), as well as referral from medical and mental health professionals working in the field of education, paediatric psychiatry, clinical psychology, and social work. The promotion materials will be hosted on the website/social media of the Department of Social Work and Social Administration and Centre on Behavioural Health of The University of Hong Kong. Screening for eligibility will be conducted by the researcher or referral professionals who have attended briefing sessions offered by the research team.

Sample Size: We expected a moderate effect size of 0.5 for the primary outcomes based on a local study [57]. Using power analysis software Gpower 3.1, assuming an attrition rate of 20%, a total sample size of 154 participants (i.e. 77 each arm) will provide 80% statistical power to detect an effect size of 0.5 in the 2-arm RCT with 4 measurement time points at 5% level of significance. For the qualitative data collection, a random subsample of 30 participating mothers will be invited to join individual, in-depth interviews at post-intervention (T₁) and 6-month follow-up (T₂). Based on various guidelines for mixed methods study design, a sample of 25 participants would suffice data saturation. If data saturation is not reached, more participants will be recruited into the study until no more new findings emerge [34].

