Group Allocation. Eligible family dyads will be randomly assigned into one of the two study conditions on a 1:1 basis using a randomization table and a computer-assisted random number

generator. The allocation list will be produced by an independent researcher and concealed from other researchers and participants until assignment.

(a) *The Dyadic Expressive Arts Group Therapy:* The 8-session intervention group (weekly session, 90 minutes each, with 3-4 dyads in 1 group) delivered will be by a registered Expressive Arts Therapist or an expressive arts therapy trainee, or a mental health professional trained in expressive arts intervention (under supervision). Each session consists of 5 basic processes in EXAT: check-in, warm-up, core art making, sharing, and closure [35]; and focuses on a specific theme related to parent-child relationship: communication, relationship, expression, empathy, interaction, love, gratitude, and connection. The program has been developed and adopted for people with ID and mothers of children having special needs and disabilities [1, 2, 36], and has been refined to integrate the cultural-relevant components (e.g. Chinese festivals, Chinese arts and music, etc.) and parent-child interaction skills and elements [2, 3]. The program has been used by the team in previous studies and community workshops [37-40]. **Appendix C** summarizes the structure of the program.

(b) *The Treatment-as-usual Waitlist Control Group*: The control group will continue with routine healthcare and social services and will be invited to participate in a similar intervention group program upon completion of the 8-month study period.

Treatment fidelity: Group facilitators participating in the intervention delivery will receive a training session covering the details of the protocol and safety precaution. Treatment fidelity will be assessed by the PI in the form of on-site or video-reviewing supervisions, preferably during the 3rd or 4th session on the condition that written consents are provided by the participants. The facilitators will receive off-site supervision provided by the PI. The assessment will be conducted using a pre-constructed observation checklist outlining the program pedagogy and the expected goals of the sessions.

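### The teacher/social-worker checklist is the one outcome from an informant outside the dyad who need not know the arm, but the plan takes no step to keep these raters unaware of it or to record whether they knew

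*Combined protocol and SAP*

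**What the plan says.** Measurements, item 9, describes a 113-item checklist scored 0, 1 or 2 per item according to the degree or frequency of each behaviour. The informant is stated: "School teachers or social workers of the participating children will be invited to fill in the checklist". Project Objectives lists it as secondary objective (vii), and it is the instrument for the behavioural and emotional part of Hypothesis 2.

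The Recruitment paragraph names community partners as a route into the trial, "including SEN schools, and community-based units that serve families of children with ID", together with referral from education, paediatric psychiatry, clinical psychology and social work, and promotion on university websites and social media. On screening it says: "Screening for eligibility will be conducted by the researcher or referral professionals who have attended briefing sessions offered by the research team". The Participants paragraph gives staff a further role in eligibility: "In the judgment of health/school professional staff, the child is capable of responding to assessments and participating in group activities".

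Under Group Allocation, the list is "concealed from other researchers and participants until assignment". For the comparator, "The control group will continue with routine healthcare and social services", with a similar programme offered after the study period. Nothing in the text says that checklist raters, or any other outcome assessors, are kept unaware of allocation after assignment. The one stated separation of staff from the intervention, in Data Analysis item 3, covers transcription of the interviews.

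**The concern.** Whether a mother and child attend weekly groups or wait is obvious to both of them. Outcomes 1 to 6 are the mother's own reports. The mood scales are completed by the child, and the face drawings (Face Stimulus Assessment, FSA) are made by the child. A teacher or social worker is the only informant who could plausibly report without knowing the arm.

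The plan leaves that to chance. A rater may hear the arm from the mother, the child, a colleague or group staff. A rater based in a referring school or unit may also have been briefed on the trial. A checklist of judged frequencies is open to expectation, and the likely direction is towards the intervention. Because awareness is not recorded, a reader could not tell a real change in behaviour from a change in how it was rated, nor judge how far this happened. Data Analysis item 3 intends to triangulate sources to assess effectiveness; that is weaker if the one outside informant shares the dyad's knowledge of arm.

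**Working it through.** **1. Who reports, who knows, what is masked**

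| Outcome | Informant or scorer | Must know the arm? | Masking stated |
|---|---|---|---|
| Items 1–6 (stress, burnout, relationship, affect, quality of life, well-being) | Mother | Yes | None |
| Item 7 (mood) | Child | Yes | None |
| Item 8 (FSA) | Drawn by child; assessment conducted by therapist, trainee or research staff | Child yes; a scorer of the drawings no | None |
| Item 9 (checklist) | Teacher or social worker | No | None |

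So the checklist is the only outcome whose informant need not know the arm. It is not the only outcome open to masked assessment: the FSA drawings are digitally scanned and could be scored without labels.

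**2. Overlap between raters and recruiters**

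Teachers and social workers rate. SEN schools, community units and social-work referrers recruit. Briefed referral professionals may screen, and health or school staff judge the child's capability. The staff groups overlap. That the same individual refers and rates is an inference. Referral and screening come before randomisation and do not in themselves reveal the arm.

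**3. Number available at follow-up**

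Inputs from Sample Size: effect 0.5 SD, 80% power, 5% level, 20% attrition, 77 per arm. Data Analysis adds two-sided testing.

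- Reproducing the plan's figure: a two-sample t-test for 0.5 SD needs 64 per arm; 64 × 1.2 = 76.8, rounded up to 77, or 154 in total. This matches. (Dividing by 0.8 instead gives 80 per arm, 160 in total.)
- After 20% loss: 77 × 0.8 = 61.6 per arm, with power of 78.6% for 0.5 SD by the t-test, close to the stated 80%.

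**4. Illustration of what rater bias would do**

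Assume no true effect and a mean shift b (in SD units) towards the intervention arising only from raters' knowledge. The noncentrality of a two-sample t-test with n per arm is b × √(n/2), and √(61.6/2) = 5.55.

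| Assumed b | Noncentrality | Chance of p < 0.05 (two-sided) |
|---|---|---|
| 0 | 0 | 5% |
| 0.1 SD | 0.55 | 8.5% |
| 0.2 SD | 1.11 | 19.6% |

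The values of b are assumptions averaged over the whole arm; the documents give none. The calculation is for one comparison at one time, not for the planned mixed-effects model over four time points with covariates, so these are not the plan's own error rates.

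**The case against.** The case on the other side has several sound parts.

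- **Silence is not disclosure.** No text says raters will be told the arm, so a reader who infers that they will know it, or that the checklist has lost its value, goes too far. A second-source rating that may be unmasked is weakened, not worthless.
- **Overlap is not stated.** A reader might infer that raters are the people who referred or screened the child. The researcher may screen, and there are other referral routes. The gap in masking exists with or without the overlap.
- **The checklist is not presented as a check on the mothers.** It is a secondary outcome about the child's behaviour, whereas the primary outcomes concern the mother's stress, burnout and perceived relationship. Even perfectly masked, it could support those only indirectly.
- **Hypothesis 2 does not rest on it alone.** Mood and emotional expression come from neither the mother nor the teacher or social worker, so it would be wrong to say that the hypothesis is left without other support.
- **The bias sizes are assumed.** The arithmetic shows sensitivity, not a forecast.
- **An analysis confined to unaware raters is not a randomised comparison.** Awareness arises after randomisation and may depend on arm and on visible improvement.

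All of this stands, and it limits the claim. It does not remove the central facts: concealment is described only up to assignment, the rating is a judgement, and nothing protects or records rater awareness.

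**Conclusion.** The point holds as a cheap and worthwhile improvement to a secondary outcome. As written, the plan leaves the behavioural part of Hypothesis 2 open to avoidable expectation bias, probably towards the intervention, and gives no means of seeing how much there was. Its size cannot be derived from the documents; under the assumed shifts of 0.1 and 0.2 SD, a nominal 5% test becomes one of about 8.5% and 20%.

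The conclusion rests on the text alone, since the CONSORT figure is not available, and on the judgement that teachers and social workers may learn the arm in ordinary contact with families or colleagues. It does not touch the primary outcomes or the sample size.

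**What to change.** 1. Send checklist forms from the research office without naming the arm.
2. Ask mothers and group staff not to tell the rater which arm the family is in.
3. Do not use as rater anyone who helps deliver the groups. Where an equally well-placed rater exists, prefer one who neither referred nor screened the child; do not exchange a rater who knows the child well for one who does not.
4. At T1, T2 and T3, add one item asking whether the rater knew or guessed the arm, and which.
5. Score the scanned FSA drawings without arm or time-point labels.
6. Keep the full randomised comparison as the analysis of the checklist and report rater awareness by arm beside it. Treat any result in unaware raters as descriptive only.

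The cost is an instruction sheet, one question per follow-up form and some file relabelling. Some raters will still learn the arm, but this will then be known. Where follow-up is already complete, the awareness question can be asked in retrospect, with its dependence on recall stated, and the lack of masking reported as a limitation.
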